5. STUDY INTERVENTIONS

5.1. Interventions, Administration, and Duration

We propose to administer the treatment in a group format to better reflect the most commonly available yoga format, and to maximize feasibility and cost-effectiveness (see also Integrity of Treatment Procedures). Providing all 3 modalities in the same sized and length group format will also maximize integrity for the comparison of the active treatment components. All three treatments will be 2 hours in duration, allowing for 15 minutes of study logistics including discussion of subject questions or difficulties with the home or group interventions, evaluation of individual subject compliance, and strategizing enhancing compliance. The treatment itself will comprise a full 105 minutes training and practice in each group session. Subjects in all 3 treatment groups will be provided with a credible rationale for the efficacy of their assigned treatment. Subjects in the CBT arm will be informed of the role of CBT in the efficacy of changing dysfunctional thought patterns and beliefs, subjects in the yoga arm will be informed of the role of yoga in changing cognitive and physical emotional and stress reactivity through the postures, breath regulation and meditation components of yoga practice, and subjects in the stress education control will be informed of the role of stress education in understanding the psychophysiological basis of stress and anxiety as a basis for overcoming stress and anxiety.

CBT: The 12 session CBT treatment will be based on the standardized protocol developed at one of our centers (CARD) and widely available [88]. An earlier version of this protocol has been empirically supported in individual and group settings [89]. This protocol is comprised of four primary treatment modules including cognitive restructuring, progressive muscle relaxation, worry exposures, and in vivo exposure exercises. See Appendix reference for CBT for GAD manual. The protocol describes session-by-session a 12-session CBT treatment. The initial sessions describe the cognitive behavioral model of worry and GAD. Each session consists of a different "lesson." These lessons initially cover basic information about the nature of the anxiety and worry, the possible function and negative consequences of worrying, the maladaptive and paradoxical effects of attempting to control and suppress one's thoughts, the basic cognitive errors of probability overestimation and catastrophic thinking, adaptive strategies to deal with worries, such as problem solving, worry exposure, which may involve exploring and exposing the patient to negative images and scenarios that might be behind some of the worrisome thoughts (e.g., a person who worries losing his or her job might be exposed to the image of sitting under the bridge as an abandoned lonely homeless person). Subjects will also be assigned to complete approximately 20 minutes of homework daily, which will be recorded in a homework log. In addition, our treatment protocol will target meta-cognitions (i.e., worrying about worrying). To target meta-cognitions, we will use treatment recommendations from Wells (2009). More specifically, the primary content of the sessions are as follows:

Session 1. Discussing the basic structure of the treatment program and logistics. Discussing commonalities among group members. The nature of generalized anxiety disorder and worry; outlining of treatment procedures and basic principles underlying treatment.

Session 2. The function of anxiety: When is it adaptive when not? Learning to recognize maladaptive anxiety.

Session 3: The purpose and function of anxiety.

Session 4: A closer look at generalized anxiety disorder.

Session 5: Basic relaxation strategies (12-step progressive muscle relaxation).

Session 6: Thoughts that cause anxiety I: Probability overestimation.

Session 7: Thoughts that cause anxiety II: Catastrophic thinking (thinking the worst).

Session 8: Thoughts that cause anxiety III: Worrying about worrying.

Session 9: From worry exposure to worry prevention.Session 10: Dealing with real problems (problem solving strategies).Session 11: Identifying obstacles in the future.Session 12: Accomplishments and future plans.

Yoga: The yoga intervention will apply Kundalini Yoga practices as taught by Yogi Bhajan. This is a well-known, accessible style of practice in the U.S. that incorporates all of the traditional components of yoga including physical postures and exercises, breathing techniques, relaxation exercises and meditation practices. It is a safe style of yoga that is registered with the Yoga Alliance that is readily and routinely adapted for therapeutic purposes. The 12-week yoga intervention will consist of 12 group classes and assigned daily home practice led by qualified and certified yoga instructors. Each group yoga session will include physical postures/exercises, breathing techniques, meditation and deep relaxation practice that are all easy to learn and do not require extensive practice or athletic ability to perform. Subjects' current physical health, flexibility and endurance will be screened at study entry. The yoga instructor will again review all preexisting conditions with subjects in the group at the beginning of the 12-week intervention and will make modifications to the practices as necessary to ensure subject safety and to prevent injury. The instructor will also require subjects to report any recent changes in their health, injuries or conditions at the beginning of every treatment session. Group size will be relatively small for yoga classes with 4-6 subjects per group, which allows for careful monitoring of subject safety during the class sessions.

Audio CD's will be provided to guide subjects through daily home practices throughout the 12-week intervention to achieve mastery and self-efficacy. The 20-minute session will begin with spinal flexibility and loosening for a physical release of tension and increased body awareness. Subjects will then practice a breathing meditation specifically recommended for coping with anxiety. In general yoga and meditation home practice compliance is reported as being feasible and equivalent to that of other behavioral interventions [74, 90, 91]. [name], a co-investigator on this study, has observed compliance in a home yoga intervention averaging 29 minutes of a daily assigned 45-minute intervention (unpublished data). We believe that we will observe adequate compliance from the proposed home intervention, and with more rigorous follow-up to encourage adherence, and expect better compliance than in our pilot trial (see preliminary data above.)

Stress Education Group (SE): SE will also include 12 weeks of group and home practice sessions. SE will control for attention from instructors, expectancy effects, and group support effects, Stress Education (SE) will be employed as an active control intervention. SE is currently used in NIH-funded protocols at the *Benson-Henry Institute for Mind-Body Medicine* at MGH. In this condition, participants will be provided with detailed and extensive information about stress and health, but will not receive any CBT, yoga, or other mind-body training techniques. Content areas will include definitions of stress and the stress response, the fight or flight response, physiological and psychological effects of stress, stress and performance, the negative stress cycle, stress and health/illness, stress and immunity, stress buffers, stress hardiness, stress and heart disease, the role of genes and environment in health, the contribution of lifestyle behaviors such as caffeine and alcohol intake and cigarette smoking, and the importance of regular exercise and proper diet (without specific instructions for exercise or dietary changes). For the daily 20 minute home practice subjects will listen to SE audio CDs containing information about nutrition

and positive perspectives on lifestyle and emotions. Therefore, we believe that comparable social and attention controls will be placed in the SE group.

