6.2.3 Blinding

Independent evaluators will remain blind to treatment assignment throughout the study. To preserve the blind they will be instructed with a reminder script for patients not to discuss their treatment prior to an assessment. The randomization codes will be created by the study statistician prior to entry of the first patient in the trial. Randomization will be stratified only by site. No unblinded analyses will be performed prior to study completion, unless specifically requested by the DSMB, in which case study PIs will only see blinded safety comparisons of the study intervention groups.

The trainers/therapists and the person handling the randomization code cannot be blinded, but they will not be involved in IE ratings, which will be used for outcomes in this trial. The PIs will supervise the treatments, and oversee all study participants including safety and adverse events. The PIs will not, however, know the subject's patient codes and the PIs will not be involved in the independent evaluator ratings. Thus these clinical and oversight study staff will not have access to data and have no influence on the outcome data. Outcome ratings will be completed by the blinded independent evaluators. The data management and analysis will be completed by the study statisticians and data manager who are not involved in clinical treatment or safety assessment at any time.

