Study personnel will be monitoring the patients' clinical and physical conditions carefully and will withdraw patients from the study if warranted by their clinical condition. The yoga instructor will again review all preexisting conditions with subjects in the group at the beginning

of the 12-week intervention and will make modifications to the practices as necessary to ensure subject safety and to prevent injury. The instructor will also require subjects to report any recent changes in their health, injuries or conditions at the beginning of every treatment session. Group size will be relatively small for yoga classes with 4-6 subjects per group, which allows for careful monitoring of subject safety during the class sessions.

In addition to the risks associated with the treatments, interviews, and questionnaires, there are some other potential risks from the electrocardiograms, such as an allergic reaction to the electrode paste. However, these reactions are rare and typically very mild.

Although every effort will be made to assure confidentiality, it is possible someone could without permission gain access to study related data during the time they are being used or stored for examination of results.

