7.5 Follow-up for Adverse Events

We will first administer the SAFTEY form at each visit. This form asks if any AE's have occurred. If the subject answers "yes" we will then fill out the cumulative AE LOG accordingly.

Adverse events will be assessed at each visit using the adverse events monitoring form and rated as mild, moderate, or severe. These parameters are defined as follows: mild (noted change in the subject's condition that causes minor distress and does not affect activity); moderate (notable distress and or mild disruption in usual activity); and severe (marked distress and/or major disruption in usual activity).

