7.6 Safety Monitoring

This study will be overseen by a study DSMB and associated DSMP, as well as the IRB at each study site. Additional monitoring by NCCAM may occur.

2. Frequency of Data Review for this Study— The frequency of data review for this study differs according to the type of data and can be summarized in the following table:

Data type	Frequency of review	Reviewer		
Summary figure of subject accrual & summary table of reasons for exclusion (based on protocol enrollment criteria)	PIs weekly for first three months of recruitment, then weekly accrual and quarterly adherence; DSMB yearly	PI, DSMB		
Summary table of status of all randomized subjects, as of date of reporting	PIs monthly, DSMB yearly	PI, DSMB		
Summary tables of adherence to IE visits and treatment sessions	PIs quarterly, DSMB yearly	PI, DSMB		
Summary table of demographic characteristics of all randomized subjects	PIs monthly, DSMB yearly	PI, DSMB		
Summary tables of all (serious) adverse events	PIs quarterly, DSMB yearly	PI, DSMB		
Detailed descriptions of SAEs	Per Occurrence	PI, DSMB, IRB, NCCAM		
Full study continuing review	Yearly	IRB (MGH, BU, and NYU respectively)		

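### Only the yoga arm has a required health and injury report at every session, and the protocol does not say whether those reports enter the adverse-event log, so by-arm counts may not be ascertained alike

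*Combined protocol and SAP*

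**What the plan says.** In the yoga arm, section 5.1 sets a check at the start of each class: "The instructor will also require subjects to report any recent changes in their health, injuries or conditions at the beginning of every treatment session". Section 7.1 repeats the requirement and adds a review at the start of the 12 weeks: "The yoga instructor will again review all preexisting conditions with subjects in the group at the beginning". In both places the check stands beside adapting the practices and preventing injury.

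AE collection is common to all arms. Section 7.5 says: "We will first administer the SAFTEY form at each visit. This form asks if any AE's have occurred". A positive answer leads to an entry in the cumulative AE log. The schedule in 6.1 has the RA completing both the SAFETY form and the AE log weekly during treatment. A footnote there says that the group leader reviews the RA's information before each class. The AE definition and the severity grades in 7.3 do not differ by arm.

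On use of the data, 7.6 lists "Summary tables of all (serious) adverse events" for the investigators quarterly and the DSMB yearly. Section 6.2.3 says that, if the DSMB asks for unblinded analyses, "study PIs will only see blinded safety comparisons of the study intervention groups".

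**The concern.** The common route is one general question. The yoga arm has a second and more specific prompt, given up to 12 times, that asks about the kind of harm expected there: section 7.1 names injury and temporary muscle soreness as risks of yoga. The descriptions of CBT and SE in 5.1 contain nothing comparable.

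Section 7.3 defines an AE as any unfavorable and unintended sign, symptom or diagnosis that is new or worse than at baseline, whoever hears of it. A sore back mentioned to the yoga instructor meets that definition. If it is logged, yoga has two ways into the log and the other arms have one. Yoga could then look less safe than it is, or a real excess of injuries could be dismissed as the result of closer questioning. The protocol presents yoga as a possible first-line option in primary care (2.2), so its harms relative to CBT will be of interest to readers.

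**Working it through.** The documents state no AE rate, so there is no figure to reproduce. The check has two parts.

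**1. Where reports can go**

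| Step | Yoga | CBT and SE |
|---|---|---|
| Weekly SAFETY form by the RA (6.1, 7.5) | yes | yes |
| AE log opened on a positive answer (7.5) | yes | yes |
| Leader sees the RA's information before class (6.1 footnote) | yes | yes |
| Session time for "discussion of subject questions or difficulties with the home or group interventions" (5.1) | yes | yes |
| Leader's log of each session (5.2) | yes, AE content not stated | yes, AE content not stated |
| Required report of health changes and injuries each session (5.1, 7.1) | yes | not described |
| Leader's information passed to the AE log | not stated | not stated |

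The sixth row is the asymmetry and the last is the gap. The only stated flow of AE information runs from the RA to the leader.

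**2. Size, under assumptions**

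Let p be the share of true events that the common form captures, equal in all arms. Let q be the share of missed events that the yoga prompt adds to the log. Both are assumed: p from 0.6 to 0.8, q from 0 to 0.5. At equal true rates:

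- recorded yoga rate / recorded comparator rate = [p + q(1 − p)] / p = 1 + q(1 − p)/p
- share of yoga's logged events found only by the extra route = q(1 − p) / [p + q(1 − p)]

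| p | q | Ratio | Share from extra route |
|---|---|---|---|
| any | 0 | 1.00 | 0% |
| 0.6 | 0.3 | 1 + 0.12/0.6 = 1.20 | 0.12/0.72 = 16.7% |
| 0.6 | 0.5 | 1 + 0.20/0.6 = 1.33 | 0.20/0.80 = 25% |
| 0.7 | 0.5 | 1 + 0.15/0.7 = 1.21 | 0.15/0.85 = 17.6% |
| 0.8 | 0.3 | 1 + 0.06/0.8 = 1.075 | 0.06/0.86 = 7.0% |
| 0.8 | 0.5 | 1 + 0.10/0.8 = 1.125 | 0.10/0.90 = 11.1% |

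In patients, suppose that a true 30% in every arm have one AE (also assumed), with p = 0.8 and q = 0.5. The recorded proportion is 0.30 × 0.8 = 24% in CBT and SE, and 0.30 × (0.8 + 0.1) = 27% in yoga. With the planned arm sizes that is 22.8 of 95 in CBT, 9.6 of 40 in SE and 25.7 of 95 in yoga.

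**The case against.** The strongest reply is that the link from instructor to log is missing. The procedure in 7.5 is the same in every arm, and 6.1 sends information the other way. If that is the whole route, q = 0 and the ratio is 1.00. A reader might infer that the counts are certainly not like for like; the text does not establish this. What stands against the reply is the definition in 7.3. Either these reports are logged, and ascertainment differs, or staff know of events that meet the definition and are absent from the record. Repeated prompting may also improve yoga patients' recall on later SAFETY forms. The protocol needs to settle the point in any case.

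Two other strong readings fail. A reader might infer that AE tables by arm go routinely to the DSMB. Section 7.6 gives no layout by arm, the comparisons in 6.2.3 depend on a DSMB request, and section 9 plans no AE comparison. A reader might also infer that events in CBT and SE are recorded only when volunteered. They are asked about weekly.

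It is also fair to say that neither the SAFETY form nor the CBT manual is reproduced. The form may already ask about health changes, and the absence of a CBT or SE prompt is read from summary descriptions. Because the leader sees the RA's information first, the yoga prompt can add only what was not reported there, which is how q is defined above.

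**Conclusion.** The difference in elicitation is real as described; its effect on AE counts is possible but not shown. Under the assumed capture rates the inflation of yoga's count per patient lies between none and one third (1.00 to 1.33). The lower end applies if instructor reports never reach the log and recall is unaffected. The upper end needs a form that misses 40% of events and a prompt that recovers half of those. The range rests on equal true rates and equal capture by the common form in all arms. No efficacy endpoint is affected and no by-arm AE analysis is prespecified, so this is a cheap improvement and not a flaw in the main analysis. Any by-arm safety comparison, at the DSMB's request or in the final report, would inherit the ambiguity, and the source of an event is hard to recover afterwards if it was not recorded.

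**What to change.** - Leave the yoga instructor's safety check as it is.
- Put the same specific question, on changes in health and new injuries or conditions, on the RA's weekly SAFETY form in all three arms, unless the form already carries it.
- State in 7.5 that an AE reported to any group leader is entered in the AE log, and add a source field (RA form, group leader, other).
- Wherever AEs are shown by arm, show them twice: for all sources, and for events elicited by the common form. The second is the closer like-for-like comparison. It cannot stand alone, because it would leave out yoga injuries told only to the instructor.

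The cost is one question, one field and a sentence or two of text, with no new visits or staff. Slightly more minor events will be logged in CBT and SE. Any recall effect of double prompting in yoga is reduced but not removed.

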5.2. Handling of Study Interventions (Treatment Integrity)

Treatment Certification and Supervision Procedures

The senior therapists who lead the CBT and yoga groups will have at least 1 year of practice in the treatment modality. Yoga instructors will have undergone a formal 200-hr yoga teacher training program, and be registered with the Yoga Alliance. CBT instructors will be clinical psychologists trained in CBT for GAD. In addition, all therapists will undergo trainings in the specific study intervention: in CBT by [name], in yoga by [name] and SE overseen by [name]. [name] has extensive expertise in both yoga, as a certified yoga instructor with over 40 years of yoga practice and instruction, and in yoga research design, as a full-time yoga researcher for over 10 years and a leading yoga research consultant and collaborator internationally. Therapists in the stress education control treatment will have been trained by the Benson Henry Institute for Mind Body Medicine stress education control intervention currently in use in ongoing studies. The training format and level for CBT and yoga will be similar to the training of therapists conducted at the Beck institute ([name] has been trained as a therapist and supervisor of CBT by the Beck Institute of Cognitive Therapy). The training will include a 3-day workshop with ongoing supervision of cases. The training procedures will consist of didactic instruction and hour-for-hour supervision of one or two concurrent training cases. Therapists-in-training will attend supervision meetings, at which both specific application and general issues of the CBT and yoga treatments will be discussed. Therapists will continue to receive weekly supervision from Drs. [name], [name] and [name], respectively, for the duration of the study, and variations in the protocol will be addressed during this weekly supervision. In the event that a therapist does not adhere to the treatment protocol or displays behavior of questionable competence, this study therapist may be asked to undergo additional training procedures before continuing as a study therapist.

Treatment Fidelity

Treatment integrity will be further insured through careful supervision and adherence monitoring of all three interventions. A random 20% of the recorded sessions of each intervention will be reviewed and fidelity ratings completed to provide feedback to the therapists/instructors using standardized adherence forms including required and prohibited elements for each intervention to prevent drift. All therapists will also complete a detailed and systematic log/report of each completed treatment session which will be reviewed in supervision along with Working Alliance Inventory.

5.3 Concomitant Interventions

Subjects will be instructed not to initiate any psychotropic medications or additional psychological interventions during the course of the study. Subjects may receive prescription medications not specifically excluded by the protocol (e.g., aspirin, cold preparations, oral contraceptives, and vitamins). Patients have to be off concurrent psychotropic medication for at least 2 weeks prior to initiation of randomized treatment, or stable on current medication for a

minimum of 6 weeks and willing to maintain a stable dose. All concomitant medication will be closely assessed and monitored in the study.

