diagnostic assessment. We conservatively estimate that 20% of eligible participants will discontinue the intervention prematurely, but all participants who are randomized will be included in the analysis with an intent to treat analytic approach. For ethical reasons, additional treatment will not be withheld for non responders (defined as CGI-I > 2) or anyone for whom additional intervention is indicated in any intervention condition during the 6 month follow up. Non responders (CGI-I>2) at week 12 will be assisted in finding appropriate care from our existing referral resources. All participants will receive 6 month assessments, but any additional treatment received by non responders will be adjusted for in the analyses.

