5.3.3 Prohibited Interventions

1) Prior experience with Yoga and/or CBT (more than 5 Yoga classes or CBT sessions within the last 3 years)

2) Current practice of mind-body techniques (e.g., yoga, meditation, Tai-Chi, etc) or CBT3) Also prohibited is any concomitant psychotherapy for GAD.

4) Initiation of anxiolytic pharmacotherapy during the 12 session treatment period is not allowed (see 8.0 exception under Intervention Discontinuation)

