9.3 Definition of Populations

Our primary analyses will use mixed-effects regression models (MRMs) with a logistic linking function (a GLMM analysis) since our primary outcome measure is dichotomous (treatment response). Analyses of secondary outcomes will be performed using MRM. MRM and GLMM easily accommodate nesting of repeated observations within subjects, include all who complete at least one assessment (including the baseline assessment), and are the preferred method to analyze longitudinal data (Hamer and Simpson, 2009 [135]). Our intent-to-treat sample includes all randomized patients who complete at least one assessment. Thus, our primary analyses (GLMM and MRM) are intent-to-treat analyses. We will also perform "per protocol" analyses. Our per protocol population will include all randomized patients who complete the baseline and post-treatment assessments, miss no more than 2 treatment sessions, who average a 4 or higher on the homework compliance scale, and who did not initiate prohibited treatment during the study. We will repeat our GLMM and MRM analyses using the per protocol sample.

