9.6 Data Analyses

Primary Analyses

Our primary analyses will use mixed-effects regression models (MRMs) with a logistic linking function (a GLMM analysis) since our primary outcome measure (response to treatment, defined as CGI-I≤2) is dichotomous. Analyses of secondary outcomes will be performed using MRM. MRM and GLMM easily accommodate nesting of repeated observations within subjects, include all subjects with at least one assessment, and are the preferred method to analyze longitudinal data (Hamer and Simpson, 2009 [135]). Since these analyses will include all subjects who are randomized and complete at least one assessment, it is an intent-to-treat analysis. Also, since subjects will undergo treatment in groups (4-6 subjects per group) our MRM and GLMM models will include 3 levels: repeated measurements (level 1) nested within subjects (level 2) who will be nested within their treatment cohort (level 3).

Our primary model will be a GLMM in which response to treatment over time will be modeled as a growth curve. Our primary analyses will examine outcomes at post-treatment (Aim 1). These analyses will include only the 7 assessments from baseline to post-treatment, and will not include the follow-up (FU) assessment since it could be affected by subjects seeking other treatments during the FU period. Only our exploratory analyses for outcome at FU (Aim 2) will include data from the FU assessment. Since recent research indicates that suboptimal modeling of the growth curve can result in incorrect results, we will examine various linear and nonlinear models to find the optimal growth curve during treatment (linear, quadratic, cubic, exponential [leveling off at an asymptote], and an ANOVA model, in which time is coded as a categorical variable. For this ANOVA model, each assessment time point is modeled with a dummy coded assessment variable [coded 1 for the assessment, 0 for other assessments]. In this model, the means at each assessment point are freely estimated and are not constrained to fit any particular pattern. See our discussion of the ANOVA model in the paragraph below for more information).We will conduct our significance tests using the growth curve that most accurately models the data (comparing the various growth curve models using AIC and BIC).

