To determine if the results of the analyses for Aim 1 are sensitive to the growth curve model, we will perform a secondary analysis, using a simple ANCOVA-type model, to verify the results of our primary growth curve model. Since the outcome is binary (response to treatment), this analysis will be performed using logistic regression, with the following predictors of outcome at post-treatment: baseline severity based on the CGI-S and SIGH-A, and the two dummy variables coding the contrast between SE and the 2 active treatments. This analysis will be performed twice: once as an ITT analysis with missing outcomes imputed as last observation carried forward, and once as a completer analysis.

Per Protocol Secondary Analysis:

As additional secondary analyses, we will repeat our GLMM and MRM analyses using the per protocol sample. We will use these analyses rather than simpler analyses (such as logistic regression or repeated measures ANOVA) because repeating our GLMM and MRMs will allow a more direct comparison to the results for the intent-to-treat sample, allows inclusion of subjects that miss some assessments (other than baseline and post-treatment), allows the modeling of complex covariances between the repeated measures, and it assumes MAR rather than MCAR.

Follow Up Secondary Analyses:

Analyses of outcome at FU (Aim 2) will be considered exploratory since subjects may seek additional treatment during follow-up. These analyses will follow the analyses of outcome at post-treatment, except one additional assessment (FU) will be added to these analyses. Since response during FU may not follow the growth curve of the treatment phase, the growth curve for Aim 2 will be modeled as "piecewise", separately modeling the growth curve during treatment and follow-up. (Analyses of the secondary outcomes at FU will follow the mixed effects ANOVA model described above since these analyses include only 4 total assessments). We will add an additional dummy variable predictor to the analyses for Aim 2, coding whether or not the subject received additional treatment during FU. We will also add the interactions of this "additional treatment" variable with all the other predictors in the analyses to determine if "additional treatment" impacted response to treatment at FU. This analysis will

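### Read literally, the per-protocol rule in 9.3 lets treatment started after week 12 decide who is in the secondary week-12 per-protocol analysis, and the sections on new treatment disagree about the period.

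*Combined protocol and SAP*

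**What the plan says.** **Which new treatment is barred, and when.** Section 5.3 is broad in scope and covers the whole study: "Subjects will be instructed not to initiate any psychotropic medications or additional psychological interventions during the course of the study". Section 5.3.3 is narrower. On drugs it reads "Initiation of anxiolytic pharmacotherapy during the 12 session treatment period is not allowed". On psychotherapy it reads "Also prohibited is any concomitant psychotherapy for GAD", with no period given.

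**What happens after week 12.** Section 3 says that, during the six-month follow-up, "additional treatment will not be withheld for non responders", and that week-12 non-responders are helped to find care. Section 7 adds that SE non-responders may choose CBT or yoga. Section 8.1 repeats the referral help and says that added treatments will be monitored and taken into account in the analyses.

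**Who is in the per-protocol sample.** Section 9.3 requires the baseline and post-treatment assessments, no more than two missed sessions, a mean homework score of at least 4, and that the patient be one "who did not initiate prohibited treatment during the study". No cut-off at week 12 is attached.

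**How the sample is used.** Section 9.6 says "we will repeat our GLMM and MRM analyses using the per protocol sample", as additional secondary analyses. It defines one sample for all time points. For the post-treatment analysis (Aim 1), 9.6 also says "These analyses will include only the 7 assessments from baseline to post-treatment", and it leaves follow-up data out because they could reflect other treatment sought in that period.

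**The concern.** The study, as the protocol describes it, includes the follow-up. Section 3 counts the six-month visit among the four blinded assessments, and the schedule in 6.1 completes the end-of-study form after that visit. A patient who starts psychotherapy or a psychotropic drug in month 4 has therefore done so during the study. Under 5.3 that is a barred treatment.

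The patients most likely to do this are the week-12 non-responders, because the protocol refers them for care. The literal rule thus works in sequence: non-response at week 12, then referral, then new treatment, then removal from the sample in which week-12 response is re-estimated. Selecting on a consequence of the outcome raises the apparent response rate. If uptake differs between arms, it also distorts the comparison between them.

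Section 9.6 keeps follow-up data out of the Aim 1 model for this very reason, yet the sample definition would let the same events back in. The stake is the credibility of the per-protocol repeat as a check on the intent-to-treat result. There is also a practical risk: two analysts could read 9.3 differently and build different samples.

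**Working it through.** **1. The planning rates.** Sections 9.2 and 9.5 give expected response of 57.9% in CBT and 22.2% in the placebo condition, used here for SE. Half the difference is (57.9 − 22.2)/2 = 17.85 points, which is the stated margin. (The text prints 56.7 beside it; 56.7 would give 17.25.) The stated 95 per arm also reproduces with 57.9%, assuming a one-sided 5% level and equal true rates: 2 × 0.579 × 0.421 × (1.645 + 0.842)² / 0.1785² = 94.6, rounded up to 95. The level is inferred, since the documents do not state it. The planning inputs are therefore 57.9% and 22.2%, with 95 and 40 patients and a planned gap of 35.7 points.

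**2. Who meets the exclusion in follow-up.**

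| Treatment started after week 12 | Under 5.3 | Under 5.3.3 |
|---|---|---|
| Anxiolytic drug | barred | not barred (12-session limit) |
| Psychotherapy for GAD | barred | arguably barred (no period given) |
| Either, as care arranged under 3, 7 or 8.1 | provided for elsewhere; not said whether it counts as prohibited for 9.3 | same |

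The sections differ in scope as well as in duration, and 9.3 does not say which of them defines prohibited treatment.

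**3. Effect of the literal rule.** Let p be the true week-12 response rate and q the share of non-responders who start treatment in follow-up and are removed. Assume that no responder is removed and that all such treatment counts as prohibited. Then

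per-protocol rate = p / [p + (1 − p)(1 − q)].

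The documents give no q, so a range is shown. At q = 50%: CBT 0.579 / (0.579 + 0.421 × 0.5) = 0.733; SE 0.222 / (0.222 + 0.778 × 0.5) = 0.363.

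| q, same in both arms | CBT | SE | Gap (points) |
|---|---|---|---|
| 0 | 57.9% | 22.2% | 35.7 |
| 25% | 64.7% | 27.6% | about 37 |
| 50% | 73.3% | 36.3% | 37.0 |
| 75% | 84.6% | 53.3% | 31.3 |

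**4. Unequal uptake.** With 50% in CBT and 80% in SE, SE becomes 0.222 / (0.222 + 0.778 × 0.2) = 58.8%, and the gap is 73.3 − 58.8 = 14.5 points. With 50% in CBT and 25% in SE, the gap is 73.3% against 27.6%, about 46 points. The distortion can go either way.

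**5. Sample left, before the other criteria.** At q = 50%, CBT keeps 95 × (1 − 0.421 × 0.5) = 75 and SE keeps 40 × (1 − 0.778 × 0.5) = 24. At q = 80%, SE keeps 40 × (1 − 0.778 × 0.8) = 15.

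**6. With a window ending at the post-treatment rating.** Later treatment removes nobody, so on this criterion the rates stay at 57.9% and 22.2% and the numbers at 95 and 40.

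**The case against.** The best defence is that exclusion is only one reading. The section that lists prohibited interventions confines new anxiolytics to the 12 sessions, and psychotherapy described as concomitant can be taken to mean alongside study treatment. Follow-up care has its own name, additional treatment, and 9.6 gives it its own indicator and interactions in the follow-up model. Every other per-protocol criterion concerns baseline through post-treatment. Care that the protocol itself arranges is hard to call prohibited. This stands as far as it goes: a reader might infer that the plan states that referred non-responders are dropped, and it does not. But the wording of 9.3 together with 5.3 leads there, and nothing in the text rules it out.

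Three further inferences go beyond the documents.

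- *That the non-inferiority conclusion is compromised.* Sections 9.2 and 9.5 specify that test with LOCF as intent to treat. The per-protocol repeat is of the GLMM and MRM models, whose coded contrasts are each active arm against SE. No per-protocol non-inferiority test is stated.
- *That SE is inflated most.* In points, CBT rises more at equal uptake of 25% (6.8 against 5.4) and 50% (15.4 against 14.1). SE rises more at 75% (31.1 against 26.7) or when its uptake is sufficiently higher. The offer of CBT or yoga to SE non-responders makes higher SE uptake plausible, but no rate is given.
- *That a large loss of the CBT–SE gap is expected.* The 14.5-point figure rests on an assumed 50%/80% split. Section 3 also allows further treatment for anyone in whom it is indicated, so some responders could be removed too, which would offset part of the inflation.

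**Conclusion.** The point holds for the secondary per-protocol analyses. Taken literally with 5.3, the rule in 9.3 makes membership of the week-12 sample depend on treatment that tends to follow from week-12 non-response. The primary intent-to-treat GLMM and the LOCF non-inferiority test are untouched.

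The size cannot be fixed from the documents. Under the stated assumptions, equal uptake of 25% to 75% would raise per-protocol response by about 7 to 27 points in CBT and 5 to 31 in SE. The CBT–SE gap would hardly change at 25% to 50% uptake, would narrow at 75%, and could shrink or grow if uptake differed by arm. This should be corrected, because the rule gives a biased result if followed as worded and the remedy is small. It does not threaten the main result.

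The disagreement between 5.3 and 5.3.3, and between 5.3 and the follow-up care in 3, 7 and 8.1, is there on any reading.

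**What to change.** In 9.3, for per-protocol analyses of post-treatment outcomes, count only prohibited treatment started between randomization and the post-treatment rating. Define the window separately for any per-protocol repeat of the follow-up analyses. There 9.6 already models additional treatment, and the literal rule would remove many of the patients whom that indicator identifies.

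Confirm that the concomitant medications/therapy log records start dates. The schedule in 6.1 lists the log weekly during treatment, at post-treatment and at follow-up, but the documents do not describe its fields.

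Separately, reconcile sections 3, 5.3, 5.3.3, 7 and 8.1 on the period during which new treatment is not allowed, and have 9.3 point to the reconciled text. Which clinical rule applies is for the investigators.

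The cost is a sentence or two in 9.3, consistent wording elsewhere and, if start dates are not yet captured, one added field. The sample size and the primary analysis do not change. The wording should be settled before treatment outcomes are unblinded.
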